## 1.0 Background

Currently in the United States, about 270,000 individuals live with SCI; roughly 12,000 new such injuries occur in the nation annually [1]. One of the most significant impairments resulting from SCI is loss of mobility. Surveys of persons with SCI indicate that mobility concerns are among the most prevalent [2], and that chief among mobility desires is the ability to stand and walk [3]. In addition to limiting access to places inaccessible by wheelchair, the inability to stand and walk impedes social inclusion and often results in a depressive psychological impact. As importantly, loss of legged mobility results in substantial secondary adverse health effects: pressure-induced skin complications; increased incidence of pain, muscle spasticity, urinary tract infections and increased body-mass index (BMI) impaired digestive, lymphatic and vascular functions; and decreased bone mineral density (BMD), respiratory, and cardiovascular capacities [4-6]. The collective effect of such impairments is a substantial decrease in quality of life and substantial increase in health care costs for individuals with SCI.

Recently, powered lower limb exoskeletons have emerged onto the landscape of rehabilitative interventions for people with spinal cord injuries (SCI). These devices have the potential to provide substantial health benefits, promote neurological and functional recovery, and allow community ambulation for individuals with SCI. Nevertheless, studies have yet to be conducted to substantiate these potential benefits.

## 2.0 Hypotheses, Aims, and Study Outline

### Prior Studies regarding Efficacy of Exoskeletons

Given the relatively recent availability of lower limb exoskeletons, little has been published on the potential health and therapeutic benefits of exoskeleton walking for non-ambulatory individuals; however, a pilot study was conducted of such walking, with 12 individuals with motor-complete thoracic-level SCI. Although that study's primary objective was to establish the safety and efficacy of the device for purposes of mobility, it anecdotally found improvements in pain, bowel and bladder function, spasticity, and emotional well-being [7]. Another small study of exoskeleton walking involving 6 subjects with motor-complete paraplegia found that all participants sustained a significant loss of fat tissue mass after 20-60 hours of use [8]. Since fat tissue mass increases the propensity for diabetes and cardiovascular disease [9], such a reduction may decrease predisposition towards these conditions.

Studies of supported standing indicate a number of health benefits for non-ambulatory individuals with SCI, including improvements in well-being, circulation, bowel and bladder function, skin integrity, and sleep, in addition to reduction in spasticity and pain [10-12]. The investigators hypothesize that, if such benefits can be derived from the stationary nature of a standing frame, substantially more dramatic health benefits can result from walking with a lower limb exoskeleton, since an exoskeleton provides a similar upright weight-bearing posture, but also provides lower limb and coordinated upper body movement, as well as cyclic weight bearing shifts from one leg to the other. Since an exoskeleton also provides mobility, and thus utility, it has the potential for much greater frequency and duration of use, relative to a standing frame, and greater dosing will likely increase the benefits of upright weight bearing.

### Hypotheses

The proposed study is intended to inform the hypotheses that (1) regular dosing of exoskeleton walking will provide health benefits to non-ambulatory and poorly-ambulatory individuals with SCI, including decreased pain and spasticity, improvements in bowel and bladder function, decreased body-mass index (BMI), enhanced well-being; (2) regular dosing of exoskeleton walking will facilitate neurological or functional recovery in some

individuals with SCI, particularly those with incomplete injuries; and (3) the level of mobility enabled by a lower limb exoskeleton is commensurate with the walking speeds, distances, and surfaces required for community ambulation.

### Study Outline

Study 1, as described herein, will assess the three hypotheses, i.e., health benefit, neurological recovery, and mobility benefits, in the context of regular dosing of exoskeleton walking in a clinical setting. These studies will be conducted at three study sites, Vanderbilt University Medical Center in Nashville TN, the James A. Haley Veterans Hospital in Tampa FL, and the Mayo Clinic in Rochester MN. All study sites will conduct an identical study protocol. The study will involve 24 non-ambulatory and poorly-ambulatory individuals with incomplete and complete SCI (i.e., 8 subjects at each site). In this study, “poorly ambulatory” is defined as persons with functional independence measure (FIM) gait score of 2 to 6 who may be able to walk short distances with or without braces and stability aid, or may be able to walk with assistance of one person, but whose primary means of mobility is a manual or power-operated wheelchair. Of the 24 individuals, half will be individuals with motor-complete injuries (i.e., American Spinal Injury Association Injury Scale, AIS, A or B), and half with motor-incomplete injuries (i.e., AIS C or D). As described subsequently in the Study Procedures section, the study will assess the therapeutic and functional effects of exoskeleton walking over an 8-week period of treatment, where the treatment consists of 3 walking sessions per week, each approximately 1.5 hours in duration for a total of 24 walking sessions. Therapeutic effects will be assessed via a number of measurements recorded primarily at study start, at the 4-week study midpoint, at the 8-week completion of treatment, and in a follow-up session, 8 weeks following the conclusion of treatment. Among the primary measurements to be used to assess secondary health benefits are dual-energy X-ray absorptiometry scans (DXA) to assess bone mineral density (BMD); Modified Ashworth scale (MAS) ratings and Spinal Cord Injury Spasticity Evaluation Tool (SCI-SET) to assess effect on spasticity; body mass to assess BMI; and a self-report questionnaire to assess effect on pain, spasticity, bowel and bladder function, skin, and well-being. Neurological effects for non-ambulatory subjects will be assessed via neurological examination and the functional reach (FR) test. Neurological effects for poorly-ambulatory subjects will additionally be assessed via the Functional Independence Measure gait score (FIM-G), the Walking Index for Spinal Cord Injury II (WISCI-II), the Ten Meter Walk Test (10MWT), and the Timed Up and Go (TUG) test, all measured while the subject is not wearing the exoskeleton. The level of mobility provided by the exoskeleton for both motor-complete and motor-incomplete injuries will be assessed by use of the FIM-G, WISCI-II, 10MWT, Six-Minute Walk Test (6MWT), TUG test, and Borg Rating of Perceived Exertion (BRPE), all measured while the subject is wearing the exoskeleton.

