## 5.0 Enrollment

Eight subjects will be recruited from the clinical practices and surrounding communities for each of the three data collection sites. Subjects will be enrolled if they satisfy the inclusion/exclusion criteria outlined above, and agree to the 18 week commitment for the study. Investigator patient lists, therapist and physician referrals, and medical record search engines will all be used to recruit potential subjects. In addition, subjects will be identified during outpatient clinical visits by study investigators. Subjects will be identified through lists and medical records. Once enrolled, subjects will be reimbursed \$25 per visit for their involvement, in addition to receiving mileage and parking reimbursement for travel to and from their trial sites.

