## 6.0 Study Procedures

### Design:

This study will include 24 non-ambulatory or poorly-ambulatory individuals with chronic SCI, i.e., at least 6 months post-injury, 12 with complete and 12 with incomplete SCI, to assess the mobility and therapeutic benefits resulting from exoskeleton use in a clinical setting. Changes in physiological and neurological status will be assessed via measurements taken pre-, mid-, and post- the 8-week intervention, as well as 8 weeks post-treatment. At all study sites, subject enrollment will begin following IRB approval, with 8 subjects enrolled at each of the 3 sites. Following IRB approval and enrollment, the study is expected to occur over an 18-month period. The treatment for each subject will consist of 31 sessions spanning 18 weeks in total, comprising a combination of 4 assessment, 3 training, and 24 treatment sessions. The 24 treatment sessions each consists of approximately 1 hour of walking in the exoskeleton, although 1.5 hours are allotted to account for donning/doffing, measurement of vital signs, skin checks, etc., and will be delivered 3 times per week over an 8-week period.

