#### Data Analysis

Table 1 lists the relationships between the outcome measures and each hypothesis. Given that each patient is in a chronic stage of injury (i.e., spontaneous changes in health and neurological status are unlikely or minimal), the investigators assume that any statistically significant change in the outcome measures between pre- and post-treatment will have resulted from treatment. Since all measures are quantitative, including the self-report and SCI-SET, testing the respective hypotheses entails testing the extent to which the pre- and post-treatment means, of respective measurements across all subjects, are different. As such, the investigators will employ paired-sample t-tests to test the extent to which pre- and post-treatment means are statistically different, by employing a 95% confidence level in the analysis, unless results indicate a more appropriate confidence level for a given set of data. In addition to using paired t-tests for validating differences in means, and establishing associated confidence levels in those differences, analysis of variance (ANOVA) methods will be employed when determining statistical significance of differences in means between multiple data sets, with 95% confidence levels. Specifically, ANOVA will be used when assessing differences in means between pre-, mid-, post-, and 8-week follow-up measurements. In addition to analyzing results across all subjects, more meaningful results will be provided by separating the subject population into appropriate groups, such as: motor-complete and motor-incomplete individuals; non-ambulatory and poorly-ambulatory ones; individuals with tetraplegia and those with paraplegia; persons with upper paraplegia and those with lower paraplegia; etc. For example, measures associated with walking while not wearing the exoskeleton will only be recorded for poorly-ambulatory individuals; neurological recovery is not expected for individuals with motor-complete injuries (while perhaps possible, such recovery is not hypothesized here); and individuals with tetraplegia are less likely to achieve walking speeds and levels of independence commensurate with community ambulation, relative to individuals with paraplegia. For these groups, ANOVA techniques will be employed to assess differences in

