means between groups, in order to indicate and validate differences in outcomes. Software packages facilitating statistical analysis will be employed, including IBM SPSS 22 and MATLAB 2014. Note that a clinical statistician is among the key study personnel associated with this proposal, as outlined in the attached organizational chart.

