Statistical Analysis Plan

Mobility and Therapeutic Benefits resulting from Exoskeleton Use in a Clinical Setting (SC140121 Study 1)

NCT03082898

[name]

H. Fort Flowers Professor of Mechanical Engineering

Professor of Electrical Engineering

Professor of Physical Medicine and Rehabilitation

[name]

[name]

[name]

Statistical Analysis Plan

Normality of data was determined for each measure by a Kolmogorov–Smirnov (KS) test. All measures were determined to be non-normally distributed, and as such are represented by median and IQR rather than mean and standard deviation. Differences in medians in all measures were tested using a Wilcoxon rank-sum test, with confidence levels for each given by corresponding p values.

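### The planned motor-complete versus motor-incomplete comparison can be partly confounded with site, because injury type is balanced only over the whole trial and no analysis includes site

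*Protocol*

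**What the plan says.** Two enrolment rules stand side by side in the protocol.

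- **Injury type, whole trial.** Study Outline: "Of the 24 individuals, half will be individuals with motor-complete injuries", the rest being motor-incomplete. The Design paragraph of section 6.0 restates this as "12 with complete and 12 with incomplete SCI".
- **Number per site.** Section 5.0: "Eight subjects will be recruited from the clinical practices and surrounding communities for each of the three data collection sites". The Design paragraph has the same rule: "with 8 subjects enrolled at each of the 3 sites". Neither place gives a mix of injury types within a site.

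Data Analysis then plans to separate the participants into groups. The list opens with "motor-complete and motor-incomplete individuals; non-ambulatory and poorly-ambulatory ones". For these groups, "ANOVA techniques will be employed to assess differences in" "means between groups, in order to indicate and validate differences in outcomes". Site is not a factor, stratum or covariate in Data Analysis or in Table 1.

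The SAP gives one test, with no stratification: "Differences in medians in all measures were tested using a Wilcoxon rank-sum test". It names no comparison of injury types.

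**The concern.** Each site recruits from its own practices and community, and its own therapists deliver the sessions and assign the spasticity scores. Case mix, amount of walking delivered and rating habits may therefore differ by site. If one site enrols mostly motor-complete participants and another mostly motor-incomplete ones, such a difference appears in the comparison of injury types, and an analysis without site cannot separate the two.

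This matters because Data Analysis treats the grouped results as more informative than the overall result, and because hypothesis 2 expects recovery mainly in incomplete injuries. A contrast between injury types would be read as evidence on that hypothesis.

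**Working it through.** **Inputs from the protocol.** 24 participants; 3 sites of 8 (3 × 8 = 24); 12 motor-complete and 12 motor-incomplete (12 + 12 = 24). The two totals agree. There is no power calculation to reproduce. The 5% level follows from the stated 95% confidence level; a two-sided test is assumed.

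**Inputs assumed.** The documents give no size for a site effect. The between-site SD is taken as 0.3 and 0.5 of the within-site SD of change, with normal change scores and no true difference between injury types.

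**1. Can group and site coincide?** Let a_i be the number of motor-complete participants at site i, so a_1 + a_2 + a_3 = 12 with each a_i from 0 to 8. There are 61 ordered splits. If every site held only one injury type, the motor-complete total would be 0, 8, 16 or 24. It is 12, so at least one site must hold both types.

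**2. How much of a site difference enters?** Site i has weight a_i/12 − (8 − a_i)/12 = (2a_i − 8)/12 in the unadjusted group difference. With d the difference between the outer sites:

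- 4/4/4: weights all 0, so 0
- 5/4/3: 2/12, so 0.17d
- 6/4/2: 4/12, so 0.33d
- 7/4/1: 6/12, so 0.50d
- 8/4/0: 8/12, so 0.67d

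No split gives more than two thirds.

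**3. How likely is each split if injury type is unrelated to site?** The number of ways is C(24,12) = 2,704,156.

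- 4/4/4: 70³ = 343,000, probability 0.127
- 5/4/3: 6 × 56 × 70 × 56 = 1,317,120, probability 0.487
- 6/4/2: 6 × 28 × 70 × 28 = 329,280, probability 0.122
- 7/4/1: 6 × 8 × 70 × 8 = 26,880, probability 0.010
- 8/4/0: 6 × 1 × 70 × 1 = 420, probability 0.0002

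Over all splits, some site is at 6:2 or worse with probability 0.386, and at 7:1 or worse with probability 0.069.

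**4. Error rate and precision.** Rejection rates come from simulation (at least 20,000 trials per split; the range spans site SD 0.3 to 0.5). The site-adjusted standard error is 1/√(Σ a_i(8 − a_i)/8), in within-site SDs. For example, 4/4/4 gives 1/√6 = 0.41 and 8/4/0 gives 1/√2 = 0.71.

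| Split | Rejects, no site term | Rejects, site in model | Adjusted SE |
|---|---|---|---|
| 4/4/4 | about 4% | 5% | 0.41 |
| 5/4/3 | 4–5% | 5% | 0.42 |
| 6/4/2 | about 6% | 5% | 0.45 |
| 7/4/1 | 7–10% | 5% | 0.52 |
| 8/4/0 | 9–17% | 5% | 0.71 |

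Weighted by the chances in step 3, the unadjusted test rejects about 5% of the time. Without a site effect, the unadjusted standard error is √(1/12 + 1/12) = 0.41, so adjustment costs no precision at 4/4/4 beyond 2 degrees of freedom. At 8/4/0 it triples the variance, because only the one mixed site informs the comparison.

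**The case against.** The strongest case against has four parts.

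- **A reader might infer that the comparison could be purely one of sites.** Step 1 rules this out, and step 2 caps the share at two thirds.
- **A reader might take 9% to 17% as the expected error rate.** That range belongs to a split with probability about 0.0002 under chance enrolment. The two most even patterns (4/4/4 and 5/4/3) together have probability 0.127 + 0.487 = 0.61 and show no inflation, and most of the 0.386 for 6:2 or worse comes from splits with about 6% error. This stands. The chances assume that the sites' patients are alike in injury type, and the documents neither support nor contradict that.
- **A reader might extend the problem to the main results.** The paired pre/post tests across all subjects are within person, so the spread of injury types over sites does not bias them. The injury-type contrast is secondary and one of several open-ended groupings. The SAP names no such contrast, so applying its rank-sum test to it is an inference.
- **The sites follow one protocol and one intervention, with manufacturer training at each, and a constant rating offset at a site cancels in change from baseline.** This also stands, but it does not close the gap. Common procedures do not equalise case mix. A site difference in treatment effect survives in change scores. The in-exoskeleton mobility measures start only during treatment, so they have no baseline to subtract.

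**Conclusion.** The concern holds as a risk of partial confounding in a secondary comparison. The protocol balances injury type only over the whole trial, and neither document includes site in an analysis. At worst two thirds of an outer-site difference would be reported as a difference between injury types.

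Under the assumed site SDs the error rate is close to nominal for the splits that chance would usually give. It becomes material only when injury type clusters by site. The plan neither prevents such clustering nor provides an analysis that would reveal or correct it.

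The documents do not support saying that the injury-type comparison will be invalid, or that the trial's pre/post findings are compromised. The sizes rest on assumed site effects, normal change scores and no dropout. This is a cheap improvement to the analysis rather than a flaw in the main results.

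**What to change.** **Analysis (the main change).** In the protocol's Data Analysis and in the SAP, state that every between-group comparison includes site as a blocking factor: a two-way ANOVA with group and site, or a rank-sum test stratified by site (van Elteren). Report a table of group by site. This keeps the error rate at 5% for every split in the ANOVA case simulated here, and it also covers the other groupings in Data Analysis, which an injury-type target would not balance. The cost is 2 degrees of freedom, and a larger standard error if the split is uneven.

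**Enrolment (only if still open).** In Study Outline, section 5.0 and the Design paragraph, add a target of 4 motor-complete and 4 motor-incomplete participants per site. Since 12/3 = 4, the totals do not change, and the adjusted standard error stays near 0.41 SD. Make it a target rather than a rigid quota, because the fit and stimulation-response criteria are narrow and a site could wait for the right injury type. The SAP is written in the past tense, so enrolment may already be over. In that case only the site-blocked comparison and the table apply, and they restore the error rate but not the precision lost to an uneven split.

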
### **3.0 Description of Intervention: The Indego Exoskeleton**

This study will employ the Indego exoskeleton (Parker Hannifin Corp), shown in Fig. 1, which is a lower limb exoskeleton that incorporates powered movement of both hip and knee joints, in addition to built-in ankle-foot-orthoses (AFOs) at both ankle joints, which provide ankle support and stability, and also transfer the weight of the exoskeleton to the ground. The Indego exoskeleton requires use of a stability aid, such as a rolling walker or set of forearm crutches. The exoskeleton enables individuals with SCI to stand, walk, and sit, and provides nominal walking speeds between approximately 0.3 and 0.6 m/s. An SCI subject is shown walking with the exoskeleton in Fig. 2. All exoskeleton walking conducted in this study will be conducted with the (contact guard) assistance of a trained physical therapist, as shown in Fig. 2.

Fig 1. Indego exoskeleton to be used in proposed study.

Fig. 2. SCI subject (T11 AIS A injury) walking with Indego exoskeleton, with assistance from physical therapist.

#### FDA Status and Device Safety

A recent study of the safety and efficacy of the Indego exoskeleton on 40 spinal-cord-injured individuals, conducted at five rehabilitation hospitals in the US, formed the basis of a 510(k) application for FDA approval of the exoskeleton. The five hospitals conducting the FDA trials were the Shepherd Center (Atlanta GA); Craig Hospital (Denver CO); the Rehabilitation Institute of Chicago (Chicago IL); Rusk Rehabilitation Hospital (New York NY); and Kessler Rehabilitation Hospital (West Orange NJ). The 510(k) application was submitted in early August 2015, and is currently under review at the FDA. The clinical evaluation report submitted with the 510(k)

application is included as an attachment with this protocol. The following discussion describing device safety was excerpted from page 38 of that report:

Over the 10 month course of the Indego clinical trial completed at the time of this filing, 40 subjects each completed the 27 sessions already described. These subjects included men and women with a wide range of characteristics. The height of the subjects ranged from 5'1" to 6'3" (155 cm to 191 cm), weight from 115lbs to 231lbs (52 kg to 105 kg), SCI level from L2 AIS C to T3 AIS A, age from 18 to 64, and time since injury from 5 months to 23 years.

All Adverse Events (AE's) were recorded during this study. An AE is defined as: "... any undesirable clinical experience (any sign, symptom, illness, abnormal laboratory value or other medical event) that occurs in a subject (or an event that worsens during the course of the study) and that could possibly be associated with the investigational product, procedure or medications required by this protocol." A Serious Adverse Event (SAE) is defined as: "... an event that is fatal or life-threatening, results in persistent or significant disability, requires intervention to prevent permanent impairment, results in hospitalization (or prolongation of hospitalization) or results in congenital anomaly or malignancy."

Out of 1,237 total study sessions completed as of July 17, 2015, there were 44 trial- related Adverse Events and 0 Serious Adverse Events. Of the 44 trial-related AE's, 19 were known to be device related. These 19 included minor instances of bruising, redness, abrasion, and swelling, as well as one instance of a rolled ankle. The causes of these events were all determined to be related to improper fitting or improper padding, except for one case of minor abrasion which was related to a padding malfunction.

**Of particular relevance for this study, no serious adverse events occurred during the 1,237 study sessions completed with the Indego during the 10-month FDA study trial.**

